3.1.1. Part A: Monotherapy Dose-escalation and Expansion

3.1.1.1. Monotherapy Dose-Escalation Cohort

The monotherapy dose-escalation portion of the trial will be conducted in up to approximately 25 subjects using the mTPI method (Ji 2010) to evaluate safety and tolerability, and to identify the MTD of SEA-BCMA. If the MTD is not reached, safety, PK, and biomarker analyses, as well as preliminary antitumor activity, will be used to determine the optimal dose. The mTPI design uses a Bayesian statistical framework and a beta/binomial hierachic model to compute the posterior probabilities of 3 intervals that reflect the relative distance between the toxicity rate of each dose level to the target DLT rate (see [Appendix C](#)). Using a target DLT rate of 25% with a 5% margin, the - 3 intervals will be (0%, 20%), (20%, 30%), and (30%, 100%), and the corresponding dosing decision rules would be:

1. Escalate if current DLT rate is most likely <20%
2. Continue if current DLT rate is most likely between 20 and 30%
3. De-escalate if current DLT rate is likely >30%

Dose finding decisions are shown in [Table 2](#). E, S, and D represent escalating the dose, staying at the same dose, and de-escalating the dose, respectively. Decision DU means that the current dose level is unacceptable because of high toxicity and should be excluded from future dosing in the trial.

Enrollment in this study will occur on a cohort-by-cohort basis. Multiple cohorts may be treated at each dose level, with a maximum of 4 subjects treated per cohort. Decisions on

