3.1.5. Dose-Limiting Toxicity

The DLT-evaluation period is the first cycle of treatment. DLTs are graded according to the National Cancer Institute's Common Terminology Criteria for Adverse Events (NCI-CTCAE), version 4.03, and defined as any of the following events during the DLT-evaluation period:

- A delay of SEA-BCMA treatment by more than 7 days due to toxicity
- Any AE \geq Grade 3, unless deemed by the SMC to be clearly unrelated to SEA-BCMA (in Parts A through D) except for the following AEs, which must meet these specified criteria to be considered a DLT:
 - Grade 4 neutropenia lasting more than 5 days

- Thrombocytopenia \geq Grade 4, or Grade 3 thrombocytopenia with clinically significant bleeding
- Anemia \geq Grade 4 unrelated to underlying disease
- Any Grade ≥ 3 tumor lysis syndrome, including associated laboratory evaluations, that is not successfully managed clinically and that does not resolve within 7 days without end organ damage
- Any \geq Grade 4 IRRs or Grade 3 IRRs that do not resolve to \leq Grade 2 within 24 hours with infusion interruption, infusion rate reduction, and/or standard supportive measures. In the event of a Grade 3 IRR in $\geq 20\%$ of subjects (ie, 2 or more in the first 10 subjects), all subsequent subjects will require premedication and/or modification of infusion approach per the recommendation of the SMC. For subjects receiving premedication, any \geq Grade 3 IRR will be considered a DLT.
- Any Grade ≥ 3 asymptomatic laboratory abnormality that does not resolve, with or without intervention, to \leq Grade 1 or the baseline grade within 72 hours
- Any treatment-related death

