3.1.9.2. Parts B, C, and D Safety Monitoring

During dose finding safety run-in cohorts in Parts B, C, and D, the SMC will review clinical data from enrolled subjects for safety assessment and for DLT determination. The SMC will make recommendations on the SEA-BCMA dose.

In addition to determination of DLTs and dose recommendations for the combination, the SMC may make 1 or more of the following recommendations during the study, as applicable:

- Recommendation or requirement of a premedication regimen as prophylaxis against IRRs
- Further evaluation of safety of SEA-BCMA on intensive dosing schedule and/or in combination with dexamethasone
- Evaluation of alternative approaches to SEA-BCMA infusion
- Evaluation of an intermediate SEA-BCMA dose on intensive dosing schedule and/or in combination cohorts
- Consideration of postremission dosing (not exceeding tested dose levels deemed tolerable)
- The recommended dose and schedule for SEA-BCMA on intensive dosing schedule and/or in combination based on the safety and activity data

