In intensive dosing weekly induction Cycles 1 and 2, if a subject has a clinically significant, unresolved AE that prevents dosing on Day 8, 15, or 22, the dose may be delayed for ≤ 3 days. On the third day, if a subject cannot receive the dose, the dose of SEA-BCMA will be eliminated and the corresponding visit will be skipped; dosing and visit schedule would resume the following week (eg, at Day 22, if Day 15 is skipped). However, if a Day 8, 15, or 22 dose is delayed for ≤ 3 days, subsequent study assessments within the same cycle will be delayed by the same number of days as the dose delay, and study drug administration for the next dose will be delayed by at least the same number of days.

During the DLT period (Cycle 1), growth factor and transfusion support is discouraged unless medically indicated; subjects who receive growth factor (eg, granulocyte colony-stimulating factor or granulocyte-macrophage colony-stimulating factor) or transfusion support (other than

red blood cell transfusions for MM-related anemia) during this period for reasons other than DLT may not be evaluable for DLT, except in Part D, where granulocyte colony-stimulating factor is permitted during Cycle 1 if given as primary or secondary prophylaxis in conjunction with pomalidomide. Consideration should be given for growth factor support for prophylaxis or treatment of cytopenias in subsequent cycles (Table 5). During dose-escalation, subjects with Grade 4 neutropenia must have a follow-up complete blood count (CBC) with differential obtained 5 days from the time of assessment for evaluation of DLT. In addition, subjects with Grade 3 asymptomatic laboratory abnormalities must have follow-up laboratory evaluation obtained 72 hours from the time of assessment for evaluation of DLT. Serum chemistry and CBCs should be collected minimally on a weekly schedule during dose delays resulting from toxicity.

Table 5 describes the recommended dose modifications for toxicity.

Table 5: Recommended dose modifications for toxicity

Toxicity	Grade 1	Grade 2	Grade 3	Grade 4
Nonhematologic (AE or laboratory abnormality)	Continue at same dose level	Continue at same dose level	Withhold dose until toxicity is \leq Grade 1 or baseline ^a , and then resume treatment at 50% of the SEA-BCMA dose	Discontinue study treatment

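### The 5-day blood count that decides the neutropenia DLT is mandated only during dose-escalation, so some events in the Part B, C and D run-ins may have undetermined duration

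*Protocol*

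**What the plan says.** **DLT definition (Protocol 3.1.5).** "The DLT-evaluation period is the first cycle of treatment". Grade 3 or higher events count "unless deemed by the SMC to be clearly unrelated to SEA-BCMA (in Parts A through D"), so the definition is written for all four Parts. Two criteria turn on duration: "Grade 4 neutropenia lasting more than 5 days", and a Grade 3 or higher "asymptomatic laboratory abnormality that does not resolve, with or without intervention, to" Grade 1 or the baseline grade inside 72 hours.

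**Follow-up tests (Protocol 5.2.3).** "During dose-escalation, subjects with Grade 4 neutropenia must have a follow-up complete blood count (CBC) with differential obtained 5 days" from the assessment. The next sentence reads: "In addition, subjects with Grade 3 asymptomatic laboratory abnormalities must have follow-up laboratory evaluation obtained 72 hours from the time of assessment". It has no phase limit of its own.

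**Terms.** Protocol 3.1.1.1 uses dose-escalation for Part A: "The monotherapy dose-escalation portion of the trial will be conducted in up to approximately 25 subjects using the mTPI method". Protocol 3.1.9.2 uses another term for the other Parts: "During dose finding safety run-in cohorts in Parts B, C, and D, the SMC will review clinical data from enrolled subjects".

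**Decision rules (Protocol 3.1.2, 3.1.3.2, 3.1.3.3).** Each six-subject run-in passes with 0 or 1 DLT.

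**Scheduled samples (Protocol 6.3.3, 6.4.3, 6.5.3).** Local blood counts and chemistry fall on Days 1, 8, 15 and 22. The visits on Days 8, 15 and 22 have windows of plus or minus 1 day.

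**SAP.** Section 4.2 defines who is DLT-evaluable but does not deal with an event of unknown duration. Sections 5.1 and 6.6.2 confine DLT summaries to dose escalation.

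**The concern.** The DLT criteria reach all Parts, but the one sample written to settle the neutropenia criterion reaches only Part A. Protocol 3.1.1.2 and 3.2.1.1 describe escalation as complete, so read literally this requirement covers none of the run-ins.

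The document history suggests how this arose. The two follow-up sentences came in with Amendment 1, before Parts B and C (Amendment 3) and Part D (Amendment 6) were added.

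DLT incidence is a primary endpoint, and a single event can change a six-subject decision. A Grade 4 neutropenia seen on Day 8 and gone by Day 15 could have lasted less or more than 5 days. The scheduled data would not show which.

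**Working it through.** The documents give no operating characteristics for the run-ins, so there is no stated figure to reproduce. The check has three steps.

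**1. Which events stay undetermined**

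Scheduled draws are nominally 7 days apart. With the plus or minus 1 day windows, Day 8 to Day 15 can be 7 − 2 = 5 to 7 + 2 = 9 days.

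- Still abnormal at the next draw: the event can be classified as exceeding the limit.
- Recovered by the next draw: whether it crossed 5 days, or 72 hours, was not observed.

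Other sampling rules fill little of this gap for neutrophils. During toxicity-related dose delays the minimum is weekly (5.2.3). In Part D, counts after Grade 4 neutropenia are weekly (Table 7).

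**2. How often a re-test would settle an event of D days**

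Assume onset is uniform within a 7-day sampling interval. The chance that the event is seen at two draws far enough apart is, limited to 0–1:

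- weekly draws alone: (D − 7)/7
- with a 5-day re-test: (D − 5)/7
- with a 72-hour re-test: (D − 3)/7

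The durations below are assumptions; the documents give none.

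| Event | D (days) | Weekly alone | With re-test |
|---|---|---|---|
| Grade 4 neutropenia | 6 | 0% | 1/7 = 14% |
| | 8 | 1/7 = 14% | 3/7 = 43% |
| | 10 | 3/7 = 43% | 5/7 = 71% |
| | 12 | 5/7 = 71% | 100% |
| | 14 | 100% | 100% |
| Laboratory abnormality | 5 | 0% | 2/7 = 29% |
| | 7 | 0% | 4/7 = 57% |
| | 10 | 3/7 = 43% | 100% |

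The re-test narrows the gap but does not close it, because onset before the first abnormal draw is unseen.

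**3. Effect on the six-subject rule**

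Let p be the true DLT rate and m the share of all DLTs that go unclassified and are counted as no DLT. With q = p(1 − m):

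P(pass) = P(at most 1 of 6) = (1 − q)^6 + 6q(1 − q)^5

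At p = 0.25 and m = 0, this is 0.178 + 0.356 = 0.534.

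| True rate p | m = 0 | m = 10% | m = 25% | m = 50% |
|---|---|---|---|---|
| 25% | 53.4% | 59.4% | 68.6% | 83.3% |
| 40% | 23.3% | 30.1% | 42.0% | 65.5% |

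At p = 25% the shift is 6.0, 15.2 or 29.9 percentage points. The share m is an assumption. It can reach 50% only if at least half of all DLTs are of the duration-based kind.

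**The case against.** The strongest reply is that the plan already has several safeguards.

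- Weekly samples classify any event that persists to the next draw.
- ALT or AST above 3 × ULN is to be repeated within 48 to 72 hours in every Part (7.7.6.3).
- On the intensive schedule, a dose held for an unresolved event can be delayed at most 3 days before it is dropped (5.2.3), which brings some laboratory results into view.
- A toxicity that delays SEA-BCMA by more than 7 days is itself a DLT.
- Unscheduled tests are not forbidden, and the SMC makes the DLT determination.
- Expansion in Parts B and C needs an SMC recommendation. In Part D it needs a data review and a protocol amendment.

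This stands as a limit on the concern. A reader might infer that duration-based DLTs cannot be judged at all in the run-ins; the documents do not support that. A reader might also infer that both re-tests are confined to Part A. The 72-hour sentence has no such limit; its shared origin with the 5-day sentence favours the narrow reading, but its wording favours the wide one.

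The reply does not remove the gap for neutrophils. No early repeat is written for them in Parts B to D, a hold of up to 3 days does not answer a 5-day question, and the SMC cannot review a sample that was never drawn.

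**Conclusion.** The point holds in a limited form. The mandated 5-day count does not extend to the run-ins, and the scope of the 72-hour re-test is ambiguous. A Grade 4 neutropenia that recovers between weekly draws may therefore be unclassifiable. On the narrower reading of the 72-hour sentence, so may a Grade 3 or higher laboratory abnormality other than ALT or AST above 3 × ULN.

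The direction of bias is conditional. A reader might infer that an event of unknown duration is not a DLT by default, but no such rule appears in either document. If the SMC does count it that way, the run-in leans towards being declared tolerable.

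The size depends on the assumed missed share: at a true rate of 25%, the pass probability rises from 53% to between 59% and 83%. A reader might take 10 points off the DLT rate, from 25% to 15%, and conclude that the pass probability rises from 53% to 78%. That treats every unclassified event as a true DLT and means that 0.10/0.25 = 40% of DLTs are missed. Nothing in the documents supports so specific a figure.

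**What to change.** 1. Reconcile Protocol 5.2.3 with 3.1.5 so that the follow-up sampling used to evaluate DLTs covers the DLT-evaluation period in every Part where those criteria apply. State explicitly which Parts the 72-hour re-test covers.
2. State in the SAP how an event of undetermined duration is counted in the six-subject rule.
3. Extend SAP 5.1 and 6.6.2 to the run-ins, and report their DLT proportions with undetermined events counted and not counted.

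The first change is a scope phrase in 5.2.3; no DLT threshold or dose changes. The cost is an occasional unscheduled local blood sample in affected subjects and one added summary, which is a new analysis because the SAP now limits DLT reporting to dose escalation. Where a sample was never drawn, items 2 and 3 can still be applied.

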5.2.4. Storage and Handling

Refrigeration should be set at 2 to 8 °C for storage of vials and solutions containing SEA-BCMA. The controlled location must be accessible only to the pharmacist, the investigator, or a duly designated person. SEA-BCMA does not contain preservatives; therefore, opened and reconstituted vials should be used as soon as possible. Please refer to the Pharmacy Instructions for further details on storage and handling.

Drug accountability procedures are provided in the Pharmacy Binder.

5.2.5. Packaging and Labeling

SEA-BCMA is supplied in clear glass vials. The clinical supplies for open-label studies are labeled as SEA-BCMA Injection. A sample label is provided in the Pharmacy Instructions.

5.2.6. Preparation

Recommended safety measures for handling and preparation include masks, protective clothing, gloves (double glove with nitrile gloves), and vertical laminar airflow safety cabinets.

Detailed drug preparation instructions are provided in the Pharmacy Instructions.

5.2.7. Continued Access to SEA-BCMA After the End of the Study

A subject deriving clinical benefit from SEA-BCMA at the time the study is completed may be permitted to continue to receive SEA-BCMA, provided the investigator considers it to be the subject's best treatment option and the study is not terminated due to safety concerns. Requests will be discussed on a subject-by-subject basis with the sponsor. If continued access to SEA-BCMA is permitted, sparse data may be collected to monitor the safety and tolerability of continued administration. Subjects will not receive SEA-BCMA beyond the protocol definition of end of treatment (EOT).

5.3. Dexamethasone

5.3.1. Description

Corticosteroids, including dexamethasone, are a key component of SOC combination regimens in MM ([Burwick 2019](#)). Dexamethasone induces apoptosis and suppresses protein synthesis in MM cell lines in vitro ([Chauhan 2002](#); [Burwick 2017](#)). In clinical trials, dexamethasone has been shown to increase the activity of several classes of drugs, including alkylating agents, IMiDs, and PIs. In addition, dexamethasone is administered as premedication for monoclonal antibodies such as daratumumab and elotuzumab (Darzalex and Empliciti prescribing information).

5.3.2. Method of Procurement

In the US, dexamethasone will be sourced by study sites from commercial supply. In other countries, oral dexamethasone will be provided to the study sites by the sponsor or dexamethasone (oral or IV) will be sourced by study sites from commercial supply.

5.3.3. Dose and Administration

Dexamethasone will be administered on Days 1, 8, 15, and 22 of each 28-day cycle.

Dexamethasone is administered as an IV infusion or PO at a dose of 40 mg. The dose of dexamethasone is 20 mg for subjects ≥ 75 years, or with BMI < 18.5 , or known to be intolerant of dexamethasone 40 mg. On days when SEA-BCMA is to be administered, dexamethasone should be administered 1 to 3 hours prior to the SEA-BCMA infusion.

5.3.4. Dose Modifications

Suggested dose modifications and supportive care by toxicity are listed in [Table 6](#).

Table 6: Recommended dose modifications for dexamethasone-related toxicity

NCI-CTCAE Category	Toxicity	Recommended Dose Modification/Supportive Care
Gastrointestinal	Grade 1 to 2 dyspepsia, gastric or duodenal ulcer, gastritis requiring medical management	Treat with a proton pump inhibitor such as omeprazole. If symptoms persist, decrease dexamethasone dose by 50%.
	≥ Grade 3 requiring hospitalization or surgery	Hold dexamethasone until symptoms are adequately controlled. Then restart at 50% of current dexamethasone dose along with concurrent therapy with a proton pump inhibitor such as omeprazole. If symptoms persist, discontinue dexamethasone and do not resume.
	Acute pancreatitis	Discontinue dexamethasone and do not resume.
Cardiovascular	≥ Grade 3 edema limiting function and unresponsive to therapy or anasarca	Diuretics as needed and decrease dexamethasone dose by 25%. If symptoms persist, decrease dose to 50% of initial dose. If symptoms continue to persist, discontinue dexamethasone and do not resume.
Neurology/ Psychiatric	≥ Grade 2 confusion or mood alteration interfering with function	Hold dexamethasone until symptoms are adequately controlled. Restart at 50% of current dose. If symptoms persist, discontinue dexamethasone and do not resume.
Musculoskeletal	≥ Grade 2 muscle weakness, symptomatic and interfering with function but not interfering with activities of daily living	Decrease dexamethasone dose by 25%. If weakness persists, decrease to 50% of initial dose. If symptoms continue to persist, discontinue dexamethasone and do not resume.
	> Grade 2 muscle weakness, symptomatic and interfering with activities of daily living	Hold dexamethasone until muscle weakness is ≤ Grade 1 or baseline. Then decrease dexamethasone dose by 25% and resume. If weakness persists, decrease dose to 50% of initial dose. If symptoms continue to persist, discontinue dexamethasone and do not resume.
Metabolic ^a	≥ Grade 3 hyperglycemia	Treatment with insulin or oral hypoglycemic agents as needed. If symptoms persist, decrease dose by 25% decrements until levels are satisfactory.
Constitutional	≥ Grade 2 insomnia	Decrease dexamethasone dose by 50%.

^a Subjects who enter the study with elevated hemoglobin A1c (HbA1c) (≥6.5%) or fasting glucose (≥126 mg/dL) at screening must be referred to an appropriate provider for glucose management prior to or within 1 week of starting study treatment in Cycle 1.

NCI-CTCAE = National Cancer Institute's Common Terminology Criteria for Adverse Events

Adverse drug reactions to dexamethasone and dexamethasone infusion/hypersensitivity reactions (IHRs) should be managed according to the approved package insert.

5.3.5. Storage and Handling

Refer to the dexamethasone package insert for storage and handling requirements.

5.3.6. Packaging and Labeling

Dexamethasone is commercially available in the US.

5.3.7. Preparation

Dexamethasone should be prepared per the package insert.

5.4. Pomalidomide

5.4.1. Description

IMiD agents such as thalidomide, lenalidomide, and pomalidomide are commonly used in early lines of therapy for MM. IMiDs enhance NK cell expansion and activity and have been shown to potentiate ADCC when combined with monoclonal antibodies. Pomalidomide is a thalidomide analogue which is approved for the treatment of RRMM in subjects who have failed prior lenalidomide therapy.

5.4.2. Method of Procurement

In the US, pomalidomide will be sourced by study sites from commercial supply.

5.4.3. Dose and Administration

Pomalidomide will be administered once daily at a dose of 4 mg PO on days 1 to 21 of each 28-day cycle. On Cycle 1 Day 1, pomalidomide should be administered 1 to 3 hours prior to SEA-BCMA infusion, to allow for appropriate timing of PK analysis. Pomalidomide should subsequently be taken at approximately the same time each day, and without food (at least 2 hours before or 2 hours after each meal). The capsules should be swallowed whole with water and not opened, broken, or chewed.

5.4.4. Dose Modifications

Suggested dose modifications and supportive care by toxicity are listed in [Table 7](#).

Table 7: Recommended dose modifications for pomalidomide-related toxicity

NCI-CTCAE Category	Toxicity	Recommended Dose Modification
Hematologic	Grade 4 thrombocytopenia, each occurrence	Withhold pomalidomide treatment and follow complete blood count weekly until thrombocytopenia improves to \leq Grade 2, then resume pomalidomide at 1 mg less than previous dose PO daily ^a .
	Grade 4 neutropenia or any grade febrile neutropenia, each occurrence	Withhold pomalidomide treatment and follow complete blood count weekly until neutropenia improves to \leq Grade 2, then resume pomalidomide at 1 mg less than previous dose PO daily ^a .
Gastrointestinal	Grade 1 or higher AST or ALT elevation, or elevation from baseline CTCAE grade	Withhold pomalidomide treatment until liver enzymes return to normal or baseline. Consider resuming pomalidomide at 1 mg less than previous dose ^a .
Other	\geq Grade 3 nonhematologic toxicity	Withhold pomalidomide treatment and follow for improvement of toxicity to \leq Grade 2, then resume pomalidomide at 1 mg less than previous dose PO daily. Permanently discontinue pomalidomide for angioedema, anaphylaxis, Grade 4 rash, skin exfoliation, bullae, or any other severe dermatologic reaction.

a If toxicities occur after dose reduction to 1 mg, discontinue pomalidomide.

ALT = alanine aminotransferase, AST = aspartate aminotransferase, CYP = cytochrome P, NCI-CTCAE = National Cancer Institute's Common Terminology Criteria for Adverse Events, PO = taken orally

If necessary to coadminister strong inhibitors of CYP1A2 in the presence of strong inhibitors of CYP3A4/5 and P-glycoprotein, consider reducing pomalidomide dose by 50%.

Dose modification guidance is based on pomalidomide prescribing information, which contains additional guidance on pomalidomide dosing.

5.4.5. Storage and Handling

Refer to the pomalidomide package insert for storage and handling requirements.

5.4.6. Packaging and Labeling

Pomalidomide is commercially available in the US.

5.4.7. Preparation

Pomalidomide should be prepared per the package insert.

5.5. Required Premedication and Postmedication for SEA-BCMA

In Parts B through D, routine premedication for infusion reactions must be administered prior to SEA-BCMA infusion per the following regimen, unless contraindicated or recommended otherwise by the SMC or medical monitor:

- Antipyretic + Antihistamine: administer approximately 45 to 90 minutes prior to SEA-BCMA infusion (required for all subjects for all doses during Cycle 1 and Cycle 2)
 - Acetaminophen, oral, 650 to 1000 mg
 - Diphenhydramine, oral or IV, 25 to 50 mg (or equivalent H1 blocker)

If no IRR is experienced during Cycle 1 or Cycle 2: one or both premedications may be omitted starting with Cycle 3 Day 1 dose.

If IRR occurs despite acetaminophen + antihistamine, treat with supportive care based on symptoms.

For monotherapy subjects (not receiving dexamethasone), add:

- Methylprednisolone, IV, 100 mg (or equivalent dosage intermediate to long-acting corticosteroid) as required premedication 1 to 3 hours prior to next SEA-BCMA infusion. If this infusion is tolerated without IRR, methylprednisolone dose may be reduced to 60 mg (or equivalent dosage of intermediate to long-acting corticosteroid), administered either oral or IV, prior to subsequent doses.
- Additional premedications (eg, H2 blockers or leukotriene inhibitors) may be considered.

For combination subjects (receiving dexamethasone), add:

- H2 blocker (famotidine 40 mg IV or equivalent) as required premedication 45 to 90 minutes prior to all subsequent SEA-BCMA doses
- Additional premedications (eg, leukotriene inhibitors) may be considered.

For management of IRRs, including recommended concomitant therapy, see Section [5.7.1](#).

There are no required postmedications for SEA-BCMA.

For Parts C and D, refer to the dexamethasone package insert for detailed information on premedication and postmedication.

